12.5 Reporting of Adverse Events and Device Deficiencies

12.5.1 **Adverse Event and Device Deficiency Classification**

All AE and DD will be reviewed by a Medtronic representative. AEs will be classified according to the definitions provided.

Upon receipt of AE at Medtronic, a Medtronic representative will review the AE/DD for completeness and accuracy and when necessary will request clarification and/or additional information from the Investigator. Medtronic will utilize MedDRA for Regulatory Activities, to assign a MedDRA term for each AE based on the information provided by the investigator.

Medtronic Business Restricted

Regulatory reporting of AEs and DDs will be completed according to local regulatory requirements. Refer to Section 12.5.2 for a list of required investigator and Medtronic reporting requirements. It is the responsibility of both to abide by any additional AE reporting requirements stipulated by the IRB responsible for oversight of the study.

AEs and DDs will be classified according to the standard definitions as outlined below:

Table 12-2: Adverse Event Classification Responsibilities

What is classified?	Who classifies?	Classification Parameters		
		Therapy-related		
Relatedness	Investigator Sponsor	Procedure-related		
		Device-related		
Seriousness	Investigator Sponsor	SAE		
Dia ana aria	Investigator	Based on presenting signs and symptoms and other supporting data		
Diagnosis	Sponsor	MedDRA term assigned based on the data provided by Investigator		

12.5.2 Adverse Event and Device Deficiency Reporting Requirements

It is the responsibility of the investigator to abide by the adverse event reporting requirements below and to also follow the reporting requirements of the IRB.

In case of an emergency or to immediately report a subject death or SADE, the investigators can contact the study team.

Table 12-3: Adverse Event and Device Deficiency Reporting Requirements

ADEs				
Investigator shall submit to:				
Medtronic	Submit in a timely manner after the investigator first learns of the effect.			
IRB	Submit to IRB per local reporting requirement.			
Sponsor Shall Submit to:				
IRB Submit to IRB per local reporting requirement.				
SADEs				
Investigator shall submit to:				

MDT18036 Version 3.0 Page 53 of 66

Medtronic	Submit in a timely manner after the investigator learns of the event or of new information in relation to an already reported event.			
IRB	Submit to IRB per local reporting requirement.			
Sponsor shall s	submit to:			
IRB	Submit to IRB per local reporting requirement.			
Investigators	Submit per local reporting requirement.			
	All other reportable AEs			
Investigator sh	all submit to:			
Medtronic	Submit in a timely manner after the investigator first learns of the event.			
IRB	Submit to IRB per local reporting requirement.			
Device Deficiencies				
Investigator shall submit to:				
Medtronic	Submit in a timely manner after the investigator first learns of the event.			
IRB	Submit to IRB per local reporting requirement.			

12.6 Subject Death

The investigator must notify Medtronic immediately and the IRB, as required, after learning of a subject's death, regardless of whether or not the death is device, procedure, or therapy-related. The investigator should also attempt to determine, as conclusively as possible, whether such deaths are related to the device system, procedure, or therapy. Deaths will be captured by a study exit eCRF and an adverse event eCRF if related to the device system, procedure, or therapy.

If an autopsy is conducted, a copy of the report should be provided to Medtronic. Medtronic requests that all device system components that were being used at the time of the death be returned to Medtronic for analysis. Requested death certificates and/or source documentation should be provided to Medtronic. If the death occurs at a location remote from the study site, it is the study site's responsibility to make every attempt to retrieve all pertinent information related to the subject's death and submit the investigator's death summary of the known events surrounding the death to Medtronic.

12.7 Product Complaint Reporting

It is the responsibility of the investigator to report all product complaint(s) associated with a medical device distributed by Medtronic, regardless whether they are related to intended use, misuse or abuse of the product. Reporting must be done immediately and via the regular channels for market-released products. The reporting of product complaints by the clinical team must be done according to the local Standard Operating Procedures. Medtronic will notify the RAs (e.g. CA) as applicable for the following incidents immediately upon learning of them and is not limited to AEs and DDs only:

> Any malfunction or deterioration in the characteristics and/or performance of a device, as well as any inadequacy in the labeling or instructions for use which led or might have

Medtronic Business Restricted

MDT18036 Version 3.0 Page 54 of 66

led to the death or serious deterioration in the state of health of a patient, user, or other person.

- Any technical or medical reason resulting in withdrawal of a device from the market by the manufacturer.
- Any serious deterioration in the state of health, including:
 - Life-threatening illness or injury
 - Permanent impairment of a body function or permanent damage to a body
 - A condition necessitating medical or surgical intervention to prevent permanent impairment of a body function or permanent damage to a body structure

13. Data Review Committees

This study will not use a Clinical Events Committee or Data Monitoring Committee.

14. Statistical Design and Methods

14.1 General Aspects of Analysis

This is a non-randomized study to characterize procedural learnings and explore effects of SCS programming on subject's pain symptoms

Continuous measures will be reported as N, means, medians, standard deviations, minimums and maximums. Categorical measures will be reported as percentages or frequency distributions. Summaries will be completed for all subjects in a given analysis set (pooled across all study sites). If hypothesis testing will be performed for a specific cohort, sample size estimates will be calculated to insure at least 80% power with a significance level of 0.05 for two-sided tests, and 0.025 for one-sided tests.

Data analysis will be performed by Medtronic-employed statisticians or designees. A validated statistical software package (e.g., SAS version 9.4 or higher) will be used to analyze the study results.

The cohort-specific Statistical Analysis Plan (SAP) will be developed prior to data analysis and will include a comprehensive description of the statistical methods to be included in the Final Clinical Study Report for that cohort. Any change to the data analysis methods described in the CIP will require an amendment only if it changes a principal feature of the CIP.

For each of the objectives the available data will be summarized and missing data will be discussed. The main analysis of the study objectives will be based on available data and missing data will not be imputed.

Medtronic Business Restricted

SCS Research Study Clinical Investigation Plan MDT18036 Version 3.0 Page 55 of 66 Medtronic

14.2 Interim Analysis

Study cohort reports will be generated when data collection has ended in the cohort and all subjects in the cohort have completed the last visit/been exited.

14.3 Primary Objective(s)

To characterize subjects' pain scores, specific to the indication associated with SCS implant, with different SCS parameters.

Hypothesis:
Endpoint definition and derivation:
Analysis Methods: Means and standard deviations of pain scores may be summarized at enrollment, follow-up, and final study visits. Pain scores may also be summarized by different subgroups, and within-subject change may also be calculated at each visit.
Determination of Subjects/Data for Analysis: All subjects who provide data at each time point will be included in the analysis (Completer's analysis) as the primary analysis of this study objective, and no imputation methods are planned for missing data.
14.4

MDT18036 Version 3.0 Page 56 of 66

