7.4 Handling of Missing, Unused, and Spurious Data and Dropouts

Missing data are a potential source of bias when analyzing study data. A rigorous study design and execution will help prevent the incidence of missing data from occurring. The analysis of the study objectives will use subjects who provide data. No imputation will be made.

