7.9.1 Primary Objective

Objective

To characterize the pain scores specific to the indication associated with SCS implant with different SCS parameters at enrollment and during follow-up periods.

Hypothesis

There is no hypothesis testing for the primary objective. The purpose of the primary objective is to characterize the pain scores by different stimulation parameter groups during follow-up periods.

Experimental design

an average overall	pain score is calculated		
		pain scores,	

Analysis method

The mean and standard deviation as well as median, min, max of the pain scores will be summarized at follow-up visits. Pain scores may also be summarized by different stimulation parameter groups. Subjects who provide data will be included in the analysis.

This document is electronically controlled

CONFIDENTIAL

This document is electronically controlled

CONFIDENTIAL

Medtronic Business Restricted 056-F286, Statistical Analysis Plan Template Rev C

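### Primary pain results are observed-case visit summaries; the visible text makes paired change and any sensitivity analysis for pain-related exits optional only

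*Protocol*

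**What the plan says.** Protocol 14.1 sets the general rule: "The main analysis of the study objectives will be based on available data and missing data will not be imputed". Protocol 14.3 applies it to the primary objective: "All subjects who provide data at each time point will be included in the analysis". The same sentence calls this a completer analysis, although the set described is everyone observed at a given visit and can change between visits.

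SAP 7.4 repeats the rule: "The analysis of the study objectives will use subjects who provide data. No imputation will be made". SAP 7.9.1 plans visit summaries: "The mean and standard deviation as well as median, min, max of the pain scores will be summarized at follow-up visits", and adds "Subjects who provide data will be included in the analysis".

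Three analyses could address exits, and each is optional:
- Within-subject change, in Protocol 14.3: "within-subject change may also be calculated at each visit". The visible part of SAP 7.9.1 does not mention it.
- Hypothesis tests of change from baseline, which the Protocol synopsis permits in some cohorts.
- Sensitivity analyses, which Protocol 14.7 lists among methods that may be used. No method or missing-data assumption is given.

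The plan does commit to some disclosure. Protocol 14.1 states: "For each of the objectives the available data will be summarized and missing data will be discussed". SAP 7.1.1 promises a disposition flow diagram, a summary of discontinuation reasons and a listing.

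**The concern.** The Protocol itself links exit to the outcome. Section 11.1.1.5 warns that study settings may be ineffective and raise pain, and 11.2 gives insufficient relief as an example of why a subject might withdraw. Section 12.1 makes lack of pain relief non-reportable as an adverse event, on the ground that pain is captured by the efficacy measures.

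A subject who leaves because a setting failed still contributes the scores given before exit. After that, the failure shows only in the disposition outputs and the missing-data discussion, not in the pain or adverse-event tables.

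The objective is to describe pain under different settings. If exit follows high pain, a setting with more such exits looks better at later visits than it was. SAP 7.4 recognises missing data as a source of bias, but its visible answer is good design and conduct, not an analysis.

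**Working it through.** **The plan's own figure.** Half-width of a 95% interval = t(0.975, N-1) × SD / √N. For N = 30 and SD = 2.5 this is 0.934, matching the 0.93 in Protocol Table 14-1 and the SAP sample-size table. The variable to which that SD belongs is not visible.

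**Simple bias formula.** Let d be the share lost and g the mean pain of leavers minus that of stayers. The full-cohort mean is (1-d) × stayers + d × leavers, so the observed mean minus the full-cohort mean is -d × g. Neither d nor g is in the documents. Assumed values:

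| Share lost | g = 1 | g = 2 | g = 3 |
|---|---|---|---|
| 10% | -0.1 | -0.2 | -0.3 |
| 20% | -0.2 | -0.4 | -0.6 |
| 30% | -0.3 | -0.6 | -0.9 |

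**Which summary is affected.** This depends on what drives exit. An illustrative simulation used 400,000 subjects, enrolment plus three follow-ups, mean 4 throughout, SD 2.5, correlation 0.6 between visits, and scores limited to 0-10; all of these are assumptions. Exit probabilities at each follow-up were:
- Level: 0.5 if the score is 7 or more.
- Worsening: 0.44 (previous score) or 0.30 (current score) if pain is 2 or more points above enrolment.
- Unrelated: 0.05.

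About 14% are lost by the last visit in every case. The model is a repeated-measures normal model with free visit means and unstructured covariance. Bias at the last visit is shown for exit driven by the previous score / by the current, unobserved score:

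| Exit driven by | Visit mean | Paired change | Model |
|---|---|---|---|
| High pain level | -0.37 / -0.46 | +0.08 / -0.09 | 0.00 / -0.23 |
| Worsening since enrolment | -0.02 / -0.10 | -0.24 / -0.31 | 0.00 / -0.20 |
| Unrelated to pain | 0.00 | 0.00 | 0.00 |

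The first row agrees with the formula. The implied gap is 0.371 / 0.141 = 2.6 points (previous score) and 0.457 / 0.141 = 3.2 points (current score), so this is selection at the strong end of the assumed range. With correlation from 0.4 to 0.8, the level-exit bias of the visit mean runs from -0.26 to -0.46 (previous) and from -0.40 to -0.49 (current).

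**Cohort size.** The documents tabulate N from 10 to 40. With level exit on the previous score, root mean squared error at the last visit, model against visit mean, is about 0.91 v. 0.84 at n = 10, 0.70 v. 0.73 at n = 15, and 0.47 v. 0.57 at n = 30. The model pays off at about 30, but not in the smallest cohorts.

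**A no-credit rule.** Giving each leaver the worse of the enrolment and last scores gives a bias of +0.26 / -0.01 under level exit and +0.23 / -0.14 under worsening exit. It can overstate pain, and it does not always go far enough.

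**The case against.** The strongest reply is that this is a framework document for a descriptive, non-randomised study. The SAP introduction and SAP 7.2 describe general methods that may be used. Under Protocol 14.1 each cohort SAP "will include a comprehensive description of the statistical methods to be included in the Final Clinical Study Report for that cohort", and it is to be written before data analysis. Cohorts also differ in settings and visit cadence. This stands as a reason not to impose a model on every cohort. It does not remove the point, because the visible overall plan does not ask cohort SAPs to deal with exits.

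A reader might infer that the plan contains no committed change or sensitivity analysis at all. The documents do not support that. Protocol 14.4 and parts of Protocol 14.3 and SAP 7.9.1 are not visible and may hold such analyses. Most row labels of Table 10-1 are also missing, so whether a pain score is taken at exit cannot be known. The synopsis shows that change from baseline is an intended, if optional, analysis.

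The exit evidence is also mixed. Protocol 11.2 names concern over battery use as well, which need not track pain, and the study procedures allow reprogramming, which gives some subjects an alternative to leaving. Exits for a related adverse event already appear in the safety tables. Missing data will be discussed and exit reasons summarised, so the risk will be partly visible, though its effect on the pain results will not be quantified.

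**Conclusion.** The point holds as a conditional one. In the visible text the primary pain results rest on observed cases at each visit, and nothing that would show their dependence on exits is more than optional. Later visit means are too low if exits follow high pain; paired change is the more biased summary if exits follow worsening; neither is biased if exits are unrelated to pain. The observed data cannot prove which case holds, so neither summary is safe alone.

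The range of 0.1-0.9 points rests wholly on the assumed 10-30% lost and 1-3 points of excess pain. A reader might infer that the visit means will understate pain, or that the bias rivals the planned precision. Neither follows. No exit rate is given, every value in the range is below 0.93, and the comparison assumes that the SD in Table 14-1 is that of the pain score. Nor would mandatory paired change or a model be a cure, as the table of biases shows.

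This is a cheap improvement of low-to-moderate priority.

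**What to change.** Keep the observed-case table as the main analysis. In SAP 7.4 and 7.9.1, require each cohort SAP with repeated pain scores to:

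1. Report paired change from enrolment beside the visit means.
2. Pre-specify one sensitivity analysis in which subjects who exit for insufficient relief or a related adverse event are not credited with benefit, for example by taking the worse of the enrolment and last scores or by counting them as non-responders. Label it sensitivity only, because it can overstate pain.
3. Where the cohort has about 30 subjects or more, add a repeated-measures model on all available scores, including enrolment, with a pre-specified covariance structure. State that it corrects only for exit explained by observed scores. Do not require it in the smallest cohorts.
4. Show discontinuations by reason next to the pain results, with insufficient relief as its own reason code if the exit form does not already have one.

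As a separate wording correction, replace the completer label in Protocol 14.3 with observed-case analysis at each visit, which matches Protocol 14.1 and SAP 7.4.

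The cost is SAP wording, a little more analysis work per cohort on data already collected, and possibly one reason code. Reported pain may look less favourable.

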10.6 Subject Consent

Investigators shall consider for enrollment all subjects who meet eligibility requirements for study participation to avoid any bias in the subject population. Prior to enrolling subjects, each investigational site's IRB will be required to approve the CIP, the informed consent form (ICF) and HIPAA/data protection authorization or other privacy language, and any other written study information to be provided to the subjects (e.g. CA Bill of Rights if applicable, subject assessments etc.). The document(s) must be controlled (i.e. version number and date) to ensure it is clear which version(s) were approved

MDT18036 Version 3.0 Page 26 of 66

by the IRB. Any adaptation of the informed consent form must be reviewed by Medtronic and approved by the IRB prior to enrolling subjects. The ICF will be provided under separate cover.

Patient informed consent is defined as legally effective, documented confirmation of a subject's voluntary agreement to participate in a clinical study after information has been given to the subject on all aspects of the clinical study that are relevant to the subject's decision to participate. The informed consent process will be performed in accordance with the ethical principles that have their origin in the Declaration of Helsinki and in accordance with 21 CRF Part 50.

Prior to entering the study, the principal investigator, or appropriately delegated designee, will explain to each subject all aspects of the clinical investigation that are relevant to the subject's decision to participate throughout the clinical investigation including, but not limited to, the following: purpose and nature of the study, study procedures, expected study duration, available alternative therapies, and the benefits and risks involved with study participation and the potential treatment.

The investigator shall seek such consent only under circumstances that provide the prospective subject sufficient opportunity to consider whether to participate, and that minimize the possibility of coercion or undue influence. No informed consent, whether oral or written, may include any exculpatory language through which the subject is made to waive or appear to waive any of the subject's legal rights, or releases or appears to release the investigator, the sponsor, the institution, or its agents from liability for negligence.

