11.2 Risk Minimization

At any time during the study, subjects will be able to turn their device OFF using their patient programmer or recharger. Furthermore, a subject has the right to withdraw from the study at any time and for any reason (eg, due to insufficient pain relief).

For patients with non-rechargeable devices, the programming settings will be closely monitored to minimize the risk of battery depletion that is sooner than their expected battery duration. It is the duration of the estimated battery duration with the proposed settings will be calculated by using the application on the clinician tablet. This time will be compared to the patient's baseline estimated battery duration. For newly implanted patients (i.e., subjects that have less than two weeks of stimulation after implantation), the baseline estimated battery duration will be calculated based on appropriate parameters and intensities used for standard-of-care programming. For patients with stable programming settings, the baseline estimated battery duration will be calculated using their baseline programming settings.

Medtronic Business Restricted

MDT18036 Version 3.0 Page 43 of 66

If the subject is determined not to be a candidate, the subject will be programmed per standard of care and exited from the study.

the estimated battery longevity will be

calculated compared to the current study settings. The programmer will compare the estimated battery duration of any new settings to that of the current programming settings and monitor current battery level.

At any point in the course of the study, the patient may exit the study and continue with their standard of care for any reason, including concern over battery usage. In addition, the current battery level and estimated battery life of the neurostimulator will be reviewed to further minimize the likelihood of any unexpected battery usage.

Further mitigations reside in careful construction of the study. This includes selecting an appropriate patient population via inclusion/exclusion screening and closely monitoring subject progress and events reported for the study. Additionally, qualified investigators with proper SCS therapy experience will be selected, which includes trained personnel to perform any additional imaging taken as a part of the study.

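### Does pooling newly implanted and stable-setting subjects in the primary analysis distort the effect of changing stimulation settings?

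*Protocol*

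**What the plan says.** Protocol 14.3 gives the analysis set for the primary objective: "All subjects who provide data at each time point will be included in the analysis". It labels this a completer analysis and takes it "as the primary analysis of this study objective, and no imputation methods are planned for missing data". The summaries are permissive: "Means and standard deviations of pain scores may be summarized at enrollment, follow-up, and final study visits", and "Pain scores may also be summarized by different subgroups, and within-subject change may also be calculated at each visit". SAP 7.1.3, 7.4 and 7.9.1 likewise use whoever provides data. SAP 7.9.1 commits to summaries at follow-up visits, with stimulation parameter group as an optional breakdown, and has no hypothesis test. The protocol synopsis allows some cohorts to test change from baseline.

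The inclusion and exclusion lists (Protocol 9.3 and 9.4) contain no minimum time on stimulation. Protocol 10.6 adds: "Investigators shall consider for enrollment all subjects who meet eligibility requirements for study participation to avoid any bias in the subject population". The synopsis defines a cohort by recommended programming and visit cadence. Protocol 14.6 says the sample is meant to characterize what happens when settings are changed.

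The two entry states are named only in Protocol 11.2, on battery life in non-rechargeable devices. For subjects with under two weeks of stimulation, "the baseline estimated battery duration will be calculated based on appropriate parameters and intensities used for standard-of-care programming". For the others: "For patients with stable programming settings, the baseline estimated battery duration will be calculated using their baseline programming settings".

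Protocol 14.1 requires a cohort-specific SAP, with a full account of methods, before any cohort's data are analyzed. The SAP's introduction calls it an overall plan, and SAP 7.2 describes its methods as general ones that might be used.

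**The concern.** For a subject on stable settings, pain at enrollment reflects the old settings and pain at follow-up the new ones, so the difference is a change of settings. For a subject in the first two weeks of stimulation, the enrollment score may fall before the therapy has taken full effect. Later improvement can then include part of the effect of starting stimulation at all.

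The visible entry rules let both kinds of subject in, cohorts are not defined by time since implant, and the primary set takes everyone with data. A pooled change could then be read as a parameter effect when part of it is not. Two parameter groups with the same true effect but different shares of new implants could also appear to differ. The sponsor draws this distinction for battery projections, while the visible pain analysis has no matching rule.

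**Working it through.** **The plan's own figure.** Table 14-1 gives a precision of 0.93 for N = 30 and SD = 2.5. Half-width = t(0.975, N−1) × SD / √N = 2.045 × 2.5 / √30 = 0.934. This agrees, as do all 25 cells of the table to rounding.

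**Inputs for the size of the effect.** N = 30 and SD = 2.5 come from that example. The quantity to which the SD belongs is blacked out, so treating it as the SD of change is an assumption. The newly implanted share w (10% to 50%) and the extra improvement d in those subjects after enrollment (1 to 3 points, central value 1.5) are not in the documents. The true settings effect is set to zero.

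**Formulas.** The shift in pooled mean change is w × d, towards improvement. The SD of the mixture is √(2.5² + w(1−w)d²). The chance that a two-sided 5% test of pooled change rejects comes from the noncentral t with 29 degrees of freedom.

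Central case: w × d = 0.3 × 1.5 = 0.45. The mixture SD is √(6.25 + 0.21 × 2.25) = 2.59.

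| Share w | Shift at d = 1 / 1.5 / 3 | Rejection at d = 1 / 1.5 / 3 |
|---|---|---|
| 10% | 0.10 / 0.15 / 0.30 | 5.5% / 6.1% / 9.2% |
| 30% | 0.30 / 0.45 / 0.90 | 9.6% / 15.1% / 38.6% |
| 50% | 0.50 / 0.75 / 1.50 | 18.0% / 33.1% / 77.7% |

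The shift equals the planned half-width when w = 0.93 / d: a share of 93% at d = 1, 62% at d = 1.5 and 31% at d = 3. Two parameter groups with shares of 10% and 50% would differ by 0.4 × d: 0.4, 0.6 and 1.2 points. In a cohort with only one entry state the shift is zero. The rejection rates matter only in a cohort that tests pooled change.

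**What separation would cost.** Suppose that, of 30 subjects, 9 are newly implanted, 6 are past two weeks but not yet settled, and 15 are stable. By simulation with d = 1.5 in the unsettled subjects, a test in the 21 subjects past two weeks rejects 10.2% of the time, and a test in the 15 stable subjects 4.9%. A two-way split would therefore not be enough. With three groups, the half-widths at SD 2.5 are 1.38 (n = 15), 1.92 (n = 9) and 2.62 (n = 6), against 0.93 pooled. A two-way split gives 1.14 (n = 21) and 1.92 (n = 9).

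**Whether the premise can be shown.** In Protocol 14.3 the entries for the hypothesis and the endpoint derivation are blacked out, and these would define the baseline. Table 10-1 has an unnamed column after Enrollment in which eligibility is checked again. Protocol 11.2 describes a point, its lead-in missing, at which a subject found not to be a candidate is exited. The synopsis speaks of change from baseline and does not name enrollment as that baseline. A separate baseline visit, or a cohort rule on time since implant, could stand in any of these places.

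**The case for a change.** The best case for a change is that nothing visible obliges anyone to separate the two entry states. The only grouping named in SAP 7.9.1 is by stimulation parameter. A descriptive mean change can be misread just as a test can, and the synopsis does allow tests. The visible rows of Table 10-1 do not list time on stimulation, and recovering it later means returning to source records. Two sentences and two dates on the enrollment form look cheap beside a rejection rate of 15% in place of 5%.

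Part of this stands. If a cohort admits both states and reports change from enrollment, the pooled figure does combine two contrasts, and an entry-state table beside it would help. The rest is weaker. Protocol 14.3 says whose data count at a visit; it does not require one merged change score. The battery text covers non-rechargeable devices only and says nothing about pain baselines. The gap in data collection is unproven: device information and medical and surgical history are recorded, and many rows of Table 10-1 are blacked out. Any workable definition of stable settings, and the choice of group for a test, would still be left to the cohort SAP.

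Nor would separation isolate the settings effect. The study is not randomized, so change in stable subjects also carries regression to the mean, expectation and the added staff contact noted in Protocol 11.3.

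**Conclusion.** No change to the protocol or the overall SAP is needed. The mixing is possible in principle, but no stated rule is shown to give a wrong result in any cohort, and the text that could settle the matter is withheld from the public copy. What remains is a level of detail that the plan assigns to the cohort-specific SAP, where a statistician who sees both entry states would ordinarily tabulate them and name the group for any test.

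Under the assumed central case the shift is 0.45 points, just under half of the 0.93 half-width. It falls to 0.10 to 0.30 at a 10% share and becomes material only where new implants are a large part of a cohort or improve by much more than a point after enrollment. These figures rest on an assumed share, an assumed early-therapy effect and an SD whose meaning is not visible. Against them, a compulsory three-way split of about 30 subjects gives intervals roughly 1.5 to 2.8 times as wide (1.38 / 0.93 and 2.62 / 0.93). Pooling with optional subgroups is a fair trade-off for a descriptive objective.
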